## 2.2.4 Performance Endpoint Analyses

#### 2.2.4.1 Technical Success

The primary analysis will be based on the TP population. The definition of technical success is provided in **Section 1.3.2.1**. The composite endpoint will be summarized as the proportion of subjects with technical success at the end of the index procedure. The count and proportion of subjects that meet the criteria of technical success will be summarized along with the 95% exact confidence interval. The individual components of the composite endpoint will also be provided.

#### 2.2.4.2 Device Success

The primary analysis will be based on the TP population. The definition of device success is provided in **Section 1.3.2.2**. The composite endpoint will be summarized as the proportion of subjects with device success at 30 days post the index procedure and scheduled follow-up visits. The count and proportion of subjects that meet the criteria of device success will be summarized along with the 95% exact confidence interval. The individual components of the composite endpoint will also be provided.

#### 2.2.4.3 Individual Patient Success

The primary analysis will be based on the IPP population. The composite endpoint will be summarized as the proportion of subjects with individual patient success at 1 year (see definition in **Section 1.3.2.3**). The count and proportion of subjects that meet the criteria of individual patient success will be summarized along with the 95% exact confidence interval. The individual components of the composite endpoint will also be provided.

Similar analyses will be provided for the TP population.

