11.4 Enrollment

The point of enrollment is the time at which a subject signs and dates the informed consent form, in accordance with ISO 14155.

Study subjects who are implanted with a permanent Tendyne Mitral Valve will be followed through two years and annually thereafter until study closure. Subjects who have any part of the Tendyne Mitral Valve System introduced into the body, but who do not end up with an implanted Tendyne Mitral Valve will be followed through one month or until any procedure or device related adverse event is resolved, whichever comes later. Subjects will then be exited from the study. Subjects who do not have any part of the Tendyne Mitral Valve System introduced into the body will be exited from the study immediately.

- LV and LA dimensions
- Effective regurgitant orifice area (EROA)
- Mitral valve gradient
- LVEF
- Cardiac output
- LVOT dimensions and gradient

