#### 1.3.3.3 Individual Patient Success

Individual patient success is a composite endpoint measured at 1 year post the index procedure, defined as device success (**Section 1.3.2.2**) and all of the following:

- No re-hospitalizations or re-interventions for heart failure
- Improvement in New York Heart Association (NYHA) functional class (≥ 1 compared to baseline)

CONFIDENTIAL Page 5 of 15

- Improvement in distance walked, 6 Minute Walk Test (6MWT) (≥ 50 meters compared to baseline)
- Improvement in Kansas City Cardiomyopathy Questionnaire scores (KCCQ) (≥ 10 compared to baseline)

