## 2.2.2 Primary Performance Endpoint Analyses

The primary performance endpoint is the proportion of subjects with mitral regurgitation (MR) grade ≤ 2, per echocardiography core laboratory, at 30 days post the index procedure. The trial is intended to demonstrate beneficial effects of the study device in reducing the MR severity in subjects treated with the Tendyne Mitral Valve System.

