### Sample Size

### **Analysis**

The primary analysis will be based on the IPP population. The endpoint will be evaluated as a proportion of subjects with MR grade  $\leq 2$  at 30 days. If the 30-day core lab assessed echocardiography data is not available, the data from the next closest visit will be used. The hypothesis will be tested by comparing the one-sided 97.5% exact lower confidence bound of the observed 30-day MR grade  $\leq 2$  rate to the performance goal of . The null hypothesis will be rejected if this lower bound is greater than

Similar analyses will be provided for the TP population.

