#### 2.5 Handling of Missing Data

**Multiplicity Issues** 

2.6

Analyses will consist of all available data as the full analysis set. Data will only be absent from analyses of study outcomes in the event that they were not available for collection.

In general, missing values in any of the endpoints will not be imputed when summarizing these endpoints using descriptive statistics. All available data collected will be used in the summaries.

CONFIDENTIAL Page 13 of 15

CL 1010439 Statistical Analysis Plan Version A

CONFIDENTIAL Page 14 of 15

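### The primary estimate of Individual Patient Success is restricted to implanted subjects, so treated subjects who leave without a valve, failures by definition, are missing from its denominator

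*SAP*

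**What the plan says.** SAP 1.3.3.3 defines the endpoint: "Individual patient success is a composite endpoint measured at 1 year post the index procedure, defined as device success" together with no heart-failure re-hospitalization or re-intervention and improvement in NYHA class, six-minute walk and KCCQ. Protocol 7.2 places it under the label of primary effectiveness. Device success (SAP 1.3.3.2, Protocol 7.1.2) requires, among other things, that the subject is alive with the intended device still in place.

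The two endpoints have different primary sets. For device success, SAP 2.2.4.2 says "The primary analysis will be based on the TP population. The definition of device success is provided in" the definitions section. For Individual Patient Success, SAP 2.2.4.3 says "The primary analysis will be based on the IPP population. The composite endpoint will be summarized" as a proportion with an exact 95% confidence interval, and then adds "Similar analyses will be provided for the TP population". Technical success (SAP 2.2.4.1) and the primary safety composite (SAP 2.2.1) also use TP as primary.

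The population definitions in SAP 1.4 are not visible. I read IPP as subjects with a completed implant (Protocol 8.5.1) and TP as subjects in whom the system entered the body (Protocol 8.5.2).

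On follow-up, Protocol 11.4 says that subjects exposed to the system "who do not end up with an implanted Tendyne Mitral Valve will be followed through one month" or until related adverse events resolve, whichever is later, and then leave the study. Protocol 14.2 agrees in substance. SAP 1.3, by contrast, has every enrolled subject followed through 5 years. On missing data, SAP 2.5 says that, in general, "missing values in any of the endpoints will not be imputed when summarizing these endpoints using descriptive statistics". Protocol 8.4 censors drop-outs without imputation.

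**The concern.** A composite and one of its required components should share a denominator unless a reason is given, and none is visible here. The subjects who fall between the two sets are not neutral omissions. Each has failed the composite on the day of the procedure, because the device-in-place condition cannot be met. Leaving them out can only raise the reported success rate.

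The study has a single arm, so no comparator carries the same exclusion. A reader of the 1-year result would naturally take it as the chance of success for a patient who undergoes the procedure. The primary analysis instead gives the chance for a patient in whom the implant was completed.

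**Working it through.** **No figure to reproduce.** The documents give no expected rate, goal or sample size for Individual Patient Success, and no expected share of treated subjects without an implant. The rates and shares below are assumptions, shown as ranges. The only document figures used are 86 (the minimum number of subjects at 12 months for the CE Mark report, SAP 1.3) and 350 (maximum enrolment, Protocol 6.3), taken here as numbers treated.

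**Step 1: status of a non-implanted subject.** Individual Patient Success requires device success, and device success requires the device in place. With no device, the outcome is failure. No 1-year measurement is needed to know this.

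**Step 2: formula.** Let N be the number treated, k the number without an implant, f = k/N, and x the number of successes, all of whom are implanted. Assume complete 1-year data in implanted subjects.

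- IPP rate = x/(N − k)
- TP rate with non-implanted subjects as failures = x/N = IPP rate × (1 − f)
- Overstatement = IPP rate × f

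**Step 3: size at an assumed IPP rate of 40%.**

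| Not implanted (assumed) | TP rate | Overstatement |
|---|---|---|
| 2% | 0.40 × 0.98 = 39.2% | 0.8 points |
| 5% | 0.40 × 0.95 = 38.0% | 2.0 points |
| 10% | 0.40 × 0.90 = 36.0% | 4.0 points |

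**Step 4: counts with 86 treated and an IPP rate near 50%** (Clopper-Pearson 95% intervals, matching the SAP's exact method).

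| Not implanted | IPP | TP, counted as failures |
|---|---|---|
| 2 | 42/84 = 50.0% (38.9 to 61.1) | 42/86 = 48.8% (37.9 to 59.9) |
| 4 | 41/82 = 50.0% (38.7 to 61.3) | 41/86 = 47.7% (36.8 to 58.7) |
| 9 | 38/77 = 49.4% (37.8 to 61.0) | 38/86 = 44.2% (33.5 to 55.3) |

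Across assumed IPP rates of about 30% to 60% and shares of about 2% to 10%, the overstatement runs from 0.7 to 6.3 points with 86 treated and from 0.6 to 6.0 points with 350.

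**Step 5: what the promised TP analysis would show.** Take 86 treated, 4 not implanted and 41 successes. If the 4 are scored as failures, TP gives 41/86 = 47.7%. If they are set aside because they have no 1-year NYHA, walk or KCCQ, TP gives 41/82 = 50.0%, identical to IPP. The visible text does not choose between these.

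**The case against.** The best defence is that the plan already promises a TP analysis. A non-implanted subject's failure is known from the procedure, so there is nothing to impute, and SAP 2.5 says that available data will be used. A reader might infer that the TP analysis necessarily loses the same people. The documents do not support that. The loss follows only if the analyst insists on 1-year component data or treats the planned early exit as a censored drop-out. SAP 1.4 and text around SAP 2.5 and 2.6 are not visible, nor are the statistical appendix sections on populations and missing data (Protocol 23.6 and 23.10), so a scoring rule may exist there. SAP 1.3 also conflicts with the one-month exit. This part of the objection stands: the visible text is silent, which is less than saying that it drops these subjects.

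It can also be said that implant failures are not hidden. Technical success, device success and primary safety all count them in TP, and the implant rate is reported (SAP 2.2.6). That is true, but it does not correct the 1-year patient-level rate.

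A reader might extend the argument to the 30-day MR endpoint. Its aim in SAP 2.2.2 is worded as "in reducing the MR severity in subjects treated with the Tendyne Mitral Valve System", while its analysis paragraph says "The primary analysis will be based on the IPP population. The endpoint will be evaluated as a proportion". The extension does not hold. MR grade 2 or lower has no device-in-place condition, so a non-implanted subject is not a failure by definition. Such subjects are followed through one month and can have a 30-day echocardiogram. The implanted set is also what Protocol 8.5.1 specifies, and a TP analysis is promised. Only the wording of the aim is out of line with the primary set.

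**Conclusion.** The point holds for Individual Patient Success. Its primary set excludes subjects who have failed by definition and differs from the set used for device success, one of its required components. The bias is always upward and equals the IPP rate times the non-implanted share: 0.8 to 4.0 points for an assumed 40% rate and 2% to 10% not implanted. With 86 treated this is smaller than the sampling uncertainty: in the example with 4 not implanted, the shift is 2.3 points and half the interval width is (61.3 − 38.7)/2 = 11.3 points. The endpoint is summarised without a hypothesis test, so neither type I error nor power is affected.

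The conclusion rests on reading IPP and TP from Protocol 8.5.1 and 8.5.2, and its size rests on rates that the documents do not give. Whether the TP analysis counts or drops these subjects is unresolved in the visible text. No change of primary set or failure rule is warranted for the MR endpoint.

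**What to change.** In SAP 2.2.4.3:

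- Make TP the primary population for Individual Patient Success and keep IPP as supportive.
- Add a rule such as: *a treated subject without the valve in place counts as a failure, whatever 1-year data exist.*

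Reconcile the follow-up statement in SAP 1.3 with Protocol 11.4 and 14.2. With the failure rule in place, the scoring of non-implanted subjects on this endpoint does not depend on how that conflict is settled.

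For MR, at most align the aim in SAP 2.2.2 with its implanted primary set.

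The population and scoring changes are SAP wording and need no new data. The cost is a slightly lower reported rate.

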#### 2.2.5 Analyses of Additional Endpoints

The additional study endpoints, described in **Section 1.3.4**, will be reported using descriptive statistics as described in **Section 2.1**.

#### 2.2.6 Device and Procedure-Related Endpoints

The following device and procedure-related acute endpoints will be reported using descriptive statistics:

Implant Rate: defined as the rate of successful delivery and deployment of Tendyne device

CONFIDENTIAL Page 12 of 15

CRD\_000\_EFS

CL1010439 Statistical Analysis Plan Version A

with echocardiographic evidence of leaflet approximation and retrieval of the delivery catheter

- Device Time: defined as the time elapsed from the start of the apex penetration to the time the tether tensioning ends
- Device Procedure Time: defined as the time elapsed from the first incision to the time of skin closure
- Fluoroscopy duration: defined as the duration of exposure to fluoroscopy during the procedure

### 2.4 Poolability of Valve Models

Two types of Tendyne valves are used in the trial: 1.0 valve and low profile (LP) valve. The LP valve design, the timeline when the LP design was introduced into the trial, and the differences in valve design and anatomical suitability between the 1.0 valve and the LP valve are described in **Section 3.4.2** of the study protocol.

All analyses described in **Section 2.2** above will be performed by pooling data of the two valve models. Analysis will also be conducted to assess poolability of the primary safety and performance endpoints, and the secondary endpoint of 30-day all-cause mortality across the valve

#### 2.5 Handling of Missing Data

**Multiplicity Issues** 

2.6

Analyses will consist of all available data as the full analysis set. Data will only be absent from analyses of study outcomes in the event that they were not available for collection.

In general, missing values in any of the endpoints will not be imputed when summarizing these endpoints using descriptive statistics. All available data collected will be used in the summaries.

CONFIDENTIAL Page 13 of 15

CL 1010439 Statistical Analysis Plan Version A

CONFIDENTIAL Page 14 of 15

